### **3.1.2 Enrollment and Accrual**

Enrollment will occur on an ongoing basis through November 1, 2020. There is no upper limit on the number of study participants, but we estimate that approximately 70 participants may be enrolled from former ITN studies and from de novo referrals. Enrollment is defined as the signing of informed consent and will be obtained prior to the initiation of any screening or study mandated procedures. Enrolled participants who do not fulfill eligibility criteria or who do not complete any mechanistic sample collection for any reason will be considered screen failures. Screening values will be considered the participant’s baseline for those who meet all eligibility criteria. If a repeat assessment is needed to confirm eligibility, the repeat value will be considered the participant’s baseline value. There is no upper limit on screen failures.

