## 1. PROTOCOL SYNOPSIS

Title	ALLTOL: A Prospective Cohort Study of Operationally Tolerant Allograft Recipients
IND Sponsor	NIAID
Conducted by	Immune Tolerance Network
Protocol Chair(s)	[REDACTED]
Accrual Objective	
There is no upper limit on the number of study participants, but we estimate that approximately 70 participants may be enrolled from former ITN studies and from de novo referrals.

Study Treatment	N/A
Study Design	
This trial is a multi-center, prospective, observational study in which operationally tolerant recipients of liver or kidney allografts will be followed longitudinally with annual collections of clinical data and biological samples. All participants will be followed for the duration of the trial regardless of changes in their tolerance status.
 
Participants will be recruited along three main pathways:
 

1. Tolerant participants from current and past ITN trials; including those who have already completed trial participation and those who are anticipated to complete trial participation;

2. Tolerant participants referred by ITN affiliated investigators, academic and community transplant physicians and directly through outreach to transplant affinity groups such as the National Kidney Foundation (NKF);

3. Tolerant participants from the general transplant community who are reachable through general media channels such as clinicaltrials.gov, the ITN website, word-of-mouth referrals from existing participants and social media.

 
Participants will be encouraged to complete their study visits on site. However, participants who are unable or unwilling to travel to a study site will have the option of completing their study visits remotely (Figure 1).

Study Duration	
The trial will continue through January 31, 2021.
 
On March 24, 2020 the study ended early due to the potential risk of the research participants and personnel as a result of the COVID-19 pandemic.

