## 4. ANALYSIS SAMPLES

The analysis sample will be comprised of all enrolled subjects that fulfill eligibility criteria and complete at least one mechanistic sample collection.

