## 7.4. Examination of Subgroups

In addition, the following subset analyses will be performed on all study endpoints where the data permits:

- a. Allograft type (liver vs. kidney)
- b. Previous ITN study participation vs. non-ITN study referral

All subgroup analyses will be descriptive in nature.

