Incidence of diabetes or use of concomitant medications for hypertension and/or hyperlipidemia	The proportion of participants that indicate that they have been newly diagnosed with diabetes (i.e. do not have diabetes at study entry) or have recorded using a medication for hypertension and/or hyperlipidemia with a corresponding two-sided 95% exact binomial confidence interval.	Analysis sample defined in Section 4

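### The diabetes and medication endpoint is one crude proportion over follow-up that can run from none to five years, so it matches no stated period and mixes new events with existing medication use

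*SAP*

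**What the plan says.** The last row of the exploratory table in SAP 7.5 is named "Incidence of diabetes or use of concomitant medications for hypertension and/or hyperlipidemia". It is summarised as a single share of participants. A person can count in either of two ways. The first is a diabetes diagnosis made since entry. The second is worded "or have recorded using a medication for hypertension and/or hyperlipidemia", and carries no such limit to new onset. For precision, the row plans to report this share "with a corresponding two-sided 95% exact binomial confidence interval". The population is the analysis sample of SAP 4. The row gives no time horizon, person-time or censoring rule.

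Four other places bear on it:

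- **Who is counted.** SAP 4 admits eligible participants who "complete at least one mechanistic sample collection". Protocol Appendix 1 schedules those samples at screening as well as at Years 1 to 5, so the screening sample is enough.
- **How long they are followed.** Protocol 3.1.2: "Enrollment will occur on an ongoing basis", with November 1, 2020 as the last date. Protocol 3.2 sets a common end of January 31, 2021. The SAP synopsis then records: "On March 24, 2020 the study ended early".
- **How it is split.** SAP 7.4 applies two subset analyses to all endpoints where the data allow: liver versus kidney, and "Previous ITN study participation vs. non-ITN study referral". Both are descriptive.
- **How the neighbouring outcome is handled.** Protocol 6.2 collects diabetes and biliary complications under the same clinical-outcomes item. SAP 7.5 gives biliary complications a delayed-entry Kaplan-Meier analysis and diabetes none.

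**The concern.** A participant seen only at screening and one seen at five annual visits each count once in this proportion, although a new diagnosis could hardly be recorded for the first. The result depends on how long people happened to be followed, and the SAP ties it to no period.

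Two features of the row add to this. The medication part has no new-onset restriction, so it counts treatment that was already in place at entry. The new-onset condition on diabetes limits the numerator only; people with diabetes at entry stay in the denominator although they cannot be newly diagnosed.

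At stake is how a descriptive result is read. A figure published as incidence, with a confidence interval, invites comparison with other cohorts and between the planned subsets, and a reader could not tell rate from follow-up or new events from existing treatment.

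**Working it through.** The plan states no rate, power or expected value for this endpoint, so there is no figure to reproduce. The check first establishes the range of follow-up, then shows what the proportion would estimate.

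**Follow-up range.** Appendix 1 gives a maximum of five scheduled years. For the minimum, a Year 1 visit in its window needs at least 365 − 60 = 305 days, about ten months. Under the protocol's dates, someone enrolled on November 1, 2020 would have had 91 days to the planned end. Under the actual closure, anyone with less than about ten months since the start of their schedule could have no in-window Year 1 visit. Zero to five years is thus what the rules allow. The documents do not report the distribution that occurred.

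**Diabetes part.** Assume a constant rate r, the same for everyone. The expected crude proportion after T years is 1 − exp(−rT):

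| Assumed rate | 1 y | 2 y | 3 y | 4 y | 5 y | Ratio, 4 y to 2 y |
|---|---|---|---|---|---|---|
| 1%/y | 1.0% | 2.0% | 3.0% | 3.9% | 4.9% | 1.98 |
| 3%/y | 3.0% | 5.8% | 8.6% | 11.3% | 13.9% | 1.94 |
| 5%/y | 4.9% | 9.5% | 13.9% | 18.1% | 22.1% | 1.90 |

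Two groups with the same rate but two and four years of follow-up would differ by a factor of 1.90 to 1.98, or 1.9 to 8.6 percentage points.

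**Pooled figure.** With follow-up uniform on 0 to 5 years (assumed) and r = 3%/y, the expected proportion is 1 − (1 − exp(−0.15))/0.15 = 7.1%. That lies between the two-year risk (5.8%) and the three-year risk (8.6%) and well below the five-year risk (13.9%). Another follow-up pattern would move it elsewhere.

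**Composite as worded.** Let a share m already take a qualifying drug at entry. If nobody starts one later, the composite is m + (1 − m)(1 − exp(−rT)). With m = 40% (assumed) and r = 3%/y:

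- 2 years: 0.40 + 0.60 × 0.058 = 43.5%
- 4 years: 0.40 + 0.60 × 0.113 = 46.8%

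The ratio falls to 1.08, and most of the figure is existing treatment. Drug starts after entry would add to the gap; the documents give no rate for them.

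**Denominator.** If 20% have diabetes at entry (assumed), then at r = 3%/y and three years, 8.6% among those at risk appears as 0.80 × 8.6% = 6.9%.

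**Does person-time remove the artefact?** Take two subsets of 35 (half of the roughly 70 expected; an illustrative split), r = 3%/y, with person-time ending at diagnosis. Person-years are 35 × (1 − exp(−rT))/r.

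- 2 years: 2.04 expected events / 67.9 person-years = 3.0 per 100
- 4 years: 3.96 expected events / 131.9 person-years = 3.0 per 100

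The crude proportions were 5.8% and 11.3%; the rates agree.

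**The case against.** The case for leaving the row alone has substance.

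- **It follows the protocol.** Protocol 3.3.4 separates endpoints worded as time to an event from this one, and the Study Definitions use incidence to mean occurrence. Protocol 9.2.2 names exact binomial intervals for proportions, though for secondary endpoints. So the row does not contradict the protocol; the argument is that a better estimate is available.
- **It is low-stakes.** The endpoint is exploratory, the subsets are descriptive, and no test or decision uses it. SAP 5.1 reports completion of each yearly visit, which gives a partial view of follow-up. Imprecision is large in any case: 5/70 is 7.1% with an exact 95% interval of 2.4% to 15.9%, and 3/35 is 8.6% with 1.8% to 23.1%.

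A reader might also infer four stronger things that the documents do not support:

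1. **That the subsets will differ through follow-up.** No follow-up distribution by organ or ITN origin is given. The risk is conditional.
2. **That the proportion understates risk over every period.** In the example, 7.1% exceeds the one-year (3.0%) and two-year (5.8%) risks and falls short only beyond about 2.5 years.
3. **That the exact interval is invalid.** If follow-up is treated as random, each outcome has the same marginal probability and the count is binomial. If it is fixed, the variance is n·p̄(1 − p̄) − Σ(pᵢ − p̄)², which is no larger than the binomial value. The fault lies in what is estimated; poor coverage is not shown.
4. **That the near-doubling applies to the reported figure.** It applies to diabetes alone. The row reads most naturally as a single composite, where existing medication use dilutes the effect.

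What survives is the lack of a defined period, the mixture of components and the denominator.

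**Conclusion.** The point holds as a minor improvement. As written, the row estimates neither a rate nor a risk at a stated time, combines new diabetes with medication use of any onset, and counts people who cannot have the diabetes event. For the diabetes part, a twofold difference in follow-up gives close to a twofold difference in the proportion at the same underlying rate: 5.8% versus 11.3% at 3%/y. For the composite the gap is smaller, 43.5% versus 46.8% under the 40% assumption.

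These sizes rest on an assumed constant rate of 1% to 5% per year, assumed follow-up patterns and assumed shares with prior medication or diabetes, none of which the documents give. Unequal follow-up follows from the design; its actual extent, and whether it differs by subset, is unknown. SAP version 1.0 is dated July 17, 2020, after the closure of March 24, 2020, so the shortened follow-up was known when the row was finalised.

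**What to change.** Split the row in SAP 7.5 into two.

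1. **New diabetes, among participants free of diabetes at entry.** Report events, person-years and the rate per person-year from enrollment with an exact Poisson interval, overall and by each subset, next to the follow-up time. Add a cumulative risk from enrollment that treats dates known only to the annual visit as interval-censored, as Protocol 9.2.2 already provides for secondary endpoints. Enrollment is the natural origin because the row defines new diagnosis relative to study entry. State one convention for person-time when only the visit interval is known, such as its midpoint.
2. **Hypertension and hyperlipidemia medication use.** Report the proportion with an exact binomial interval at entry and at each annual visit, with the number seen at that visit as the denominator. Protocol 5.2 already documents medication at each visit.

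The cost is a few lines of SAP text and modest programming, with no new data collection: entry status, annual outcome review and visit medication are all in Appendix 1. Intervals will be wide at about 70 participants, and wider by subset. SAP 10 should record the change, since the protocol lists this as one endpoint.

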## 8. SAFETY EVALUATION

### 8.1. Overview of Safety Analysis Methods

All safety analyses will be carried out using all enrolled subjects unless otherwise noted. Missing safety information will not be imputed.

### 8.2. Adverse Events

Only serious adverse events (SAEs) are collected. All SAEs will be classified by system organ class (SOC) and preferred term, according to a standardized thesaurus (Medical Dictionary for Regulatory Activities [MedDRA] version 19.0). The severity of SAEs will be classified using the National Cancer Institute's (NCI's) Common Toxicity Criteria for Adverse Events (CTCAE) version 4.03. Each SAE is entered on the electronic case report form (eCRF) once at the highest severity. As such, no additional data manipulation is needed to identify events.

An overall summary table will be developed to report the number of events and the number and percentage of subjects having at least one event in the following categories:

- SAEs with an outcome of death
- SAEs related to study mandated blood draw

In addition, SAEs classified by MedDRA SOC and preferred term will be summarized for all SAEs.

Summary tables will present the total number of events as well as the number and percentage of subjects experiencing the events. If a subject experiences the same SAE on multiple occasions, the event will be counted once for each occurrence when reporting the number of SAEs. When reporting the number of subjects experiencing the events, a subject will only be counted once if they experience an event within the particular SOC or preferred term. Percentages will be based on the number of enrolled subjects.

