## 8.4 COLLECTION AND RECORDING OF SERIOUS ADVERSE EVENTS

### 8.4.1 Collection Period

Serious adverse events will be collected from the time of first study blood draw until 30 days after the subject prematurely withdraws (without withdrawing consent), is withdrawn from the study, or completes the study.

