## 5. STUDY SUBJECTS

### 5.1. Disposition of Subjects

The disposition of all enrolled subjects will be summarized in tables and listed.

The numbers and percentages of subjects enrolled, screen failed, and accrued will be presented. The number and percent completing each yearly study visit as well as reasons for

early termination from the study will be presented. The breakdown of allograft type (liver vs. kidney) and previous ITN study participation vs. non-ITN study participation will also be shown.

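### SAP 8.2 divides SAE counts by all enrolled subjects, so any enrolled subject who never had a protocol-mandated blood draw dilutes the percentage

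*SAP*

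**What the plan says.** SAP 8.1 sets the safety population: "All safety analyses will be carried out using all enrolled subjects unless otherwise noted". SAP 8.2 notes no exception and fixes the denominator for SAE tables: "Percentages will be based on the number of enrolled subjects".

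Protocol 3.1.2 says who is enrolled: "Enrollment is defined as the signing of informed consent and will be obtained prior to the initiation of any screening or study mandated procedures". The same section keeps screen failures within the enrolled group. They are enrolled people found ineligible, or those "who do not complete any mechanistic sample collection for any reason will be considered screen failures". It adds: "There is no upper limit on screen failures".

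Protocol 8.4.1 sets when safety collection starts: "Serious adverse events will be collected from the time of first study blood draw". Protocol 8.2.3 ties a study SAE to a blood draw in one of two ways. Either the event is serious and falls within 24 hours of the mandated research draw, or it falls outside that period and the site investigator considers it possibly or definitely associated with a mandated draw.

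**The concern.** The numerator and denominator describe different groups. The numerator can come only from people who had a protocol-mandated draw. The denominator is everyone who signed consent.

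Protocol 1.3.1.1 limits the risk of participation to the yearly sample collection and describes only harms of blood drawing. SAP 8.2 gives SAEs related to the mandated draw their own row in the overall summary table. The percentage in that row is the study's main statement of procedural risk, and a procedural risk should be expressed per person who underwent the procedure. Including people who did not can only move the figure down.

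**Working it through.** The plan states no SAE rate, SAE count or screen-failure count, so there is no figure to reproduce. The check has two parts: whether the mismatch follows from the definitions, and how large it could be.

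**Definitions side by side**

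1. *Could enrolled in the SAP simply mean accrued?* No. SAP 5.1 treats them as separate counts: "The numbers and percentages of subjects enrolled, screen failed, and accrued will be presented".
2. *Can an enrolled subject be undrawn?* Yes. Consent comes before any procedure (Protocol 3.1.2), and Visit 0 may follow up to 60 days later (Protocol 6.1.1). Under Appendix 1, footnote 2, someone screened remotely must satisfy every criterion except confirmed graft function before a sample visit is scheduled. A remote candidate who fails another criterion therefore stops before that visit.
3. *Can an undrawn subject have a study SAE?* No. Both routes in Protocol 8.2.3 need a mandated draw, and Protocol 8.4.1 starts collection at the first one.
4. *Does any section restrict the SAE denominator to drawn subjects?* No. Protocol 9.2.7 asks only for frequencies and proportions, so the denominator comes from the SAP alone.

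**Size**

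Let N be the number enrolled, u the number enrolled but never drawn, s = u/N, and x the number of subjects with an SAE.

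- Reported percentage = x/N
- Percentage among those at risk = x/(N − u)
- Reported ÷ at-risk = (N − u)/N = 1 − s

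N = 70 is the enrolment estimate in Protocol 3.1.2 and 9.3. The values of s are assumptions, with u rounded to whole subjects.

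| Assumed s | u | Drawn, 70 − u | Factor (70 − u)/70 | x = 1: reported → at-risk | x = 3: reported → at-risk |
|---|---|---|---|---|---|
| 0% | 0 | 70 | 1.000 | 1.43% → 1.43% | 4.29% → 4.29% |
| 5% | 4 | 66 | 0.943 | 1.43% → 1.52% | 4.29% → 4.55% |
| 10% | 7 | 63 | 0.900 | 1.43% → 1.59% | 4.29% → 4.76% |
| 20% | 14 | 56 | 0.800 | 1.43% → 1.79% | 4.29% → 5.36% |
| 30% | 21 | 49 | 0.700 | 1.43% → 2.04% | 4.29% → 6.12% |
| 40% | 28 | 42 | 0.600 | 1.43% → 2.38% | 4.29% → 7.14% |

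For one affected subject the gap runs from 1.52 − 1.43 = 0.09 to 2.38 − 1.43 = 0.95 percentage points. The factor 1 − s does not depend on N, so the relative understatement is the same if fewer than 70 were enrolled.

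**The case against.** The strongest reply is that the undrawn group may be very small or empty. Appendix 1 places the clinical laboratory tests and the mechanistic blood collection at the same screening visit. A candidate who fails on graft function has had blood taken, and Protocol 6.3 has abnormal results repeated. A remote candidate may have the sample visit before graft function is confirmed. Some unsuitable candidates may also be turned away before consent by the web screening tool in Protocol 3.1.1. All of this stands, and it limits the size. A reader might infer that every screen failure dilutes the percentage. The documents do not support that, because only undrawn screen failures do.

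A second reply is that readers can correct the figure themselves, since SAP 8.2 tabulates counts of events and subjects and SAP 5.1 gives screen-failure totals. This stands in part. Those totals mix drawn and undrawn subjects, so they do not yield the right denominator.

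A third reply is that no decision depends on the percentage. There is no comparison arm, and Protocol 3.4 sets no stopping rules. This is correct and keeps the point minor.

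A reader might also infer that the plan will report too low an upper confidence limit for SAE risk. It will not, because neither SAP 8.2 nor Protocol 9.2.7 plans an interval for SAEs. With no SAEs the planned tables show 0% under either denominator.

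**Conclusion.** The mismatch is real and follows from the documents' own definitions. If any enrolled subject was never drawn and at least one SAE occurs, the SAE percentage is too low by the factor 1 − s. With 70 enrolled and an assumed s of about 5% to 40%, one affected subject is reported as 1.43% where the figure among drawn subjects is about 1.5% to 2.4%. The documents do not give s, so the true size is unknown and probably small. It is zero if s = 0 or if no SAE occurs.

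Two stronger readings should be avoided. The estimate of about 70 is an enrolment figure, so it should not be read as 70 drawn subjects with screen failures added on top. The mismatch also does not show that the population in SAP 8.1 is wrong. That population also governs the deaths listing (SAP 8.3) and the laboratory summaries (SAP 8.4), which are not tied to a blood draw in the way a study SAE is. Restricting it could drop an enrolled subject's death from the listing.

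**What to change.** Change only the last sentence of SAP 8.2, for example to: *Percentages of subjects with SAEs will be based on subjects who had at least one protocol-mandated blood draw, including screen failures who were drawn.* The analysis sample in SAP 4 is not a substitute, because it leaves out ineligible subjects who were drawn and so were at risk.

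State in the same place whether a screening draw for clinical laboratory tests alone counts. Protocol 8.2.3 refers at one point to draws for research specimens, while Protocol 8.4.1 refers to study draws generally. Appendix 1, footnote 4, allows the hematology sample to fall on a different date from the mechanistic collection, so such a draw is foreseeable. The rule chosen should agree with both protocol sections.

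Add the number of enrolled subjects never drawn to the disposition table in SAP 5.1. Leave SAP 8.1 and the deaths listing on all enrolled subjects.

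The cost is one revised sentence, one clarification and one extra table row. SAE percentages become slightly less favourable if any enrolled subject was undrawn.

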### **8.3. Deaths**

A listing summarizing death, including time of death and cause of death, will be created.

### **8.4. Clinical Laboratory Evaluation**

Clinical laboratory measurements include serum chemistry, urinalysis, hematology, and a fasting lipid panel. Results will be converted to standardized units where possible.

Laboratory data for ALT and GGT will be plotted to show patterns over time for liver recipients. Creatinine and urine albumin-creatinine ratio will be plotted for kidney recipients. Glucose and fasting lipid data will be plotted for all subjects. Data will be plotted as a spaghetti plot where each subject's values will be plotted and connected by line segments, forming one line per subject. For all labs listed above, descriptive statistics of both absolute values and percent change from baseline will be presented in tabular format.

